As a robustness check for these secondary analyses, we will estimate a joint model that combines the likelihood from the treatment failure survival model with the likelihood of the longitudinal mixed model for the secondary outcomes.^{18,19} A joint model of the likelihood enables unbiased estimation of the treatment effect on the longitudinal outcomes while accounting for potentially informative missingness due to treatment failure, where longitudinal measures might be missing not at random (MNAR). We propose to fit a joint model using a Bayesian Monte-Carlo Markov Chain (MCMC) approach implemented in the JMBayes2 R package.²⁰ We will report results of the joint model with a particular focus on the effect of treatment on differences in the longitudinal outcome, accounting for the treatment failure process. We note that since JADAS scores, drug levels, and antibody levels are measured infrequently in the trial: at 3 months (JADAS only), 6 months, 12 months, and time of treatment failure, that it might be difficult or impossible to fit longitudinal models that include a random effect for slope (required by currently implemented joint modeling software, such as JMBayes2). We will assess MCMC parameter convergence using standard diagnostics (trace and density plots of model parameters, Gelman-Rubin convergence statistics) and will report any

failure to converge.

3.1.2 Specific Aim 2

Primary Analysis

As emphasized earlier, the data available in this clinical trial provide an opportunity to assess the capacity of selected variables in predicting a uveitis flare in both treatment groups. Exploratory analyses will be conducted as follows.

Descriptive tabulation and plotting of all outcome variables with respect to each potential explanatory variable will be reported.

Univariate log binomial regression of the occurrence of a uveitis flare during the first 12 months will be examined. The following predictors (i.e. regressors) will be examined:

- baseline blood serum levels of myeloid-related protein MRP8/14 (calprotectin),
- baseline serum levels of erythrocyte sedimentation rate (ESR),
- baseline serum levels of C reactive protein,
- baseline ADA levels,
- baseline anterior chamber cell level (Grade 0 or 0.5),
- randomization group,
- age,
- sex,
- race,
- Tanner stage for pubertal stage,
- baseline antimetabolite use,
- duration of control of uveitis (MOP Section 2.4.1) before baseline,
- length of time taking adalimumab before baseline,
- country

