For continuous outcomes, plots of each measurement along with the outcome status will be prepared for each patient. Plots will include data for patients after any treatment failure, in a different color. We plan to separately examine patients using antimetabolites at baseline and those who were not. We will conduct linear mixed effects regression for these longitudinal outcomes, using time dependent covariates. The continuous variables of interest are:

- BCVA
- CHAQ score
- EYE-Q score
- JADAS-10 and JADAS-27 scores

Application of LASSO procedures to linear mixed models will be conducted with the R package `glmmlasso`.

Finally, a similar exploratory analysis will be used for the time to treatment failure (as defined earlier), again using LASSO regression with the same set of covariates. LASSO model selection will be implemented using the R package `coxnet`. We note that other model selection procedures (such as backwards stepwise regression) can be considered, provided uncorrected significance P-values are not reported after model selection.

3.1.3 Specific Aim 3

Primary analysis. The outcome variable is the proportion of people achieving corticosteroid-sparing controlled ocular inflammation at month 12 of the study. We propose log binomial regression, with randomization group as a covariate and fixed effects for baseline antimetabolite use and country. The analysis will follow the same template as in Specific Aim 1 for analysis of binary outcomes (including assessment of homogeneity by country). A linear binomial regression, with the identity link, will be used to calculate risk differences between groups. Significance will be assessed with a two-sided alpha of 0.05. The distinction between the analyses in Aims 1 and 3 are that in Aim 1, outcomes are reported at 6 and 12 months, censoring at treatment failure, while in Aim 3, outcomes are reported by intent-to-treat at 6 and 12 months, regardless of treatment changes in the event of treatment failure. We propose to use Firth bias correction in this log binomial regression, and additional information is provided below.

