3.3 Sample Size Estimation

3.3.1 Primary Calculation

A sample size of 118 subjects (59 in each group) provides 88% power to detect a hazard ratio of 2.0 for the time to treatment failure comparing the group randomized to discontinue adalimumab to the group randomized to continue using adalimumab, assuming a median time until treatment failure of 10 weeks in the group that discontinues adalimumab (Arm 1) and of 20 weeks in the group that continues on adalimumab (Arm 2), an equal allocation between groups, and a 10% total loss to follow-up.

For sample size planning, we use the approximate formula given in Friedman et al (2010) for the number in each group:

$$N = \frac{(Z_\alpha + Z_\beta)^2 (\phi(\lambda_C) + \phi(\lambda_I))}{(\lambda_I - \lambda_C)^2}$$

Where λ denotes the rate in the intervention arm (λ_I) and control arm (λ_c), $\phi(\lambda) = \lambda^2 / 1 - e^{-\lambda T}$ at censoring time T , and Z_α, Z_β are quantiles from the standard normal distribution at power (1- β) and significance level α .

In a retrospective study by our group of JIA-associated uveitis patients on immunomodulatory therapies (antimetabolites, cyclosporine, TNF- α inhibitors, or combination therapy), 37% of patients attempted to stop treatment after achieving corticosteroid-sparing control of inflammation.²³ Of patients who stopped TNF- α inhibitors, nearly 50% experienced a recurrence of inflammation within 100 days after stopping treatment. Approximately 80% of patients had a recurrence of ocular inflammation within one year after stopping treatment.

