Furthermore, a retrospective study of uveitis patients on infliximab showed that patients with JIA-associated uveitis who attempted to stop anti-TNF- α therapy after achieving control of inflammation experienced recurrence of inflammation after a median of 76 days.²⁴ Similarly, in a small retrospective study outside our group, 6 pediatric uveitis patients flared between 3 and 7 months after discontinuing adalimumab.²⁵ Based on these data, we can expect to observe a majority of treatment failures within the first 6 months and nearly all treatment failures by Month 12 among patients randomized to discontinue adalimumab treatment. It is important to note that stopping infliximab treatment involves a gradual taper of the dose over the course of several weeks. In both studies, time to recurrence of inflammation was measured from the start of the taper rather than the point at which patients had completely stopped the medication. Because discontinuing adalimumab treatment does not involve a taper in our trial, we expect the time to recurrence of inflammation to be shorter as compared to infliximab. Therefore, we anticipate time to treatment failure of 10 weeks in patients randomized to discontinue adalimumab in ADJUST.

Table 3. Previous time-to-event uveitis studies

Author	Population	Median Time to Uveitis Relapse
Acharya et al. (2018)	JIA-associated uveitis patients who discontinued TNF- α (n = 11)	100 days
Shakoor, Esterberg, & Acharya (2014)	JIA-associated uveitis patients who discontinued infliximab (n = 18)	76 days

Castiblanco, Meese, & Foster (2016)	Uveitis pediatric patients who discontinued adalimumab	3 to 7 months (range)
-------------------------------------	--	-----------------------

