In a clinical trial of JIA-associated uveitis patients with active inflammation on a stable dose of antimetabolite, 114 patients were randomized to adalimumab or placebo biweekly subcutaneous injections and followed for up to 18 months.²⁶ The mean duration of sustained inactive disease was 179.3 ± 16.9 days in the adalimumab treatment group (vs. 14.5 ± 23.9 days in the placebo group). An open label long-term follow-up study of non-infectious adult uveitis patients treated with adalimumab demonstrated that, among patients with inactive disease who entered the study, over 90% of patients still had inactive disease at week 54.²⁷ At 78 weeks, 74% still had inactive disease.²⁸ Given the available evidence on disease recurrence for patients on long-term adalimumab treatment, we can expect a lower recurrence rate and longer time to treatment failure in patients continuing on adalimumab compared to those discontinuing treatment. While these studies suggest that most uveitis patients on adalimumab remain inflammation-free greater than one year, we have conservatively estimated 20 weeks to be the median time to treatment failure among patients randomized to continue adalimumab treatment.

Thus, 118 patients total (59 per group), provides 88% power to detect a hazard ratio of 2.0 for the time to treatment failure, assuming a 10% loss to follow-up. We assume an alpha of 0.05 (two sided). Adjusting for country in our analyses is assumed to give us even greater power. A power table is provided in Table 4 below, varying the median time until treatment failure (in weeks).

Table 4: Total Sample Size Based on Median Time to Treatment Failure for Stopping vs. Continuing Adalimumab

		80% Power	90% Power
Stopping Treatment Versus Continuing Treatment	8 weeks vs 16 weeks	92	124
	10 weeks vs 20 weeks	96	126
	12 weeks vs 24 weeks	98	130

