- **The proportion of people with macular edema.** We anticipate at most 1% of the individuals continuing treatment to develop macular edema, given its absence at baseline. We anticipate approximately 80% power to detect a difference of 15% (in absolute terms) in macular edema in the discontinuation arm (given 118 subjects).

The analyses for censoring at 6 months are similar to 12 months, with small decreases in detectable effect sizes due to assuming slightly shorter follow-up by month 12.

3.3.2.2 Specific Aim 2

Specific Aim 2 is exploratory, and is hypothesis generating. However, we present selected power analyses to illustrate the sufficiency of the sample size of the trial—fixed in Specific Aim 1—to inform regression models of the exploratory outcomes in Specific Aim 2.

For modeling the effect of the potentially predictive biomarker MRP8/14, we assume a

median split as a guide to power. Assuming approximately 50 uveitis flares among our patient population, we anticipate 80% power to detect a difference in MRP8/14 levels of 140 ng/ml (assuming a standard deviation of 250 ng/ml, based on previous studies).^{35,36}

For modeling the number of missed study treatment doses in the first 12 months, we anticipate over 80% power to detect a difference of 2.8 missed doses between the discontinuation and continuation groups (assuming 118 patients enrolled, and a standard deviation of 5).

For the time to failure outcome within 12 months, we anticipate 88% power to detect a hazard ratio of 2.0 between patients taking antimetabolites at baseline and those not using antimetabolites, assuming approximately equal numbers in each group (assuming 10% loss to follow-up).

3.3.2.3 Specific Aim 3

Primary Analysis

The proportion of people who achieved corticosteroid-sparing controlled ocular inflammation (Table 2) by month 6 of the study based on treatment intervention. For sample size planning, we assume a test of proportions between the two randomization groups. Based on prior research, we assume that 30% of those who discontinue adalimumab will have controlled ocular inflammation by month 6.²⁴ We anticipate over 80% power to detect a 29% difference between the two groups, based on 118 subjects.

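### Aim 2 opens with single-predictor yes/no models of 12-month flare that carry no term for randomized arm; per-predictor Cox models with arm would use the same data with clearly more power

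*SAP*

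**What the plan says.** SAP 2.3.2 names the principal Aim 2 outcome as treatment failure within 6 and within 12 months. It lists predictors of uveitis recurrence, and of time to treatment failure, as secondary objectives.

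SAP 3.1.2, under its primary-analysis heading, uses a different outcome: "Univariate log binomial regression of the occurrence of a uveitis flare during the first 12 months will be examined". Fourteen predictors follow, including MRP8/14, ESR, C-reactive protein, antibody level, antimetabolite use, duration of control and randomization group. Because the models are univariate, no biomarker is adjusted for arm at this step.

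Multivariable selection comes next: LASSO, stepwise and elastic net, with interactions with arm explored. Arm is a candidate there and is not stated to be forced in. At the end of the section the SAP adds: "Finally, a similar exploratory analysis will be used for the time to treatment failure (as defined earlier"). That step is a LASSO Cox model on the same covariates, and no per-predictor Cox models are described.

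On power, SAP 3.3.2.2 states: "For the time to failure outcome within 12 months, we anticipate 88% power to detect a hazard ratio of 2.0", for antimetabolite users against non-users in roughly equal groups. For MRP8/14 it assumes about 50 flares. It gives no hazard-ratio power for the 12-month yes/no model.

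**The concern.** SAP 3.3.1 expects "nearly all treatment failures by Month 12 among patients randomized to discontinue adalimumab treatment". If nearly everyone has the event by month 12, a yes/no outcome at month 12 separates patients poorly. What distinguishes a high-risk patient is then mainly how early failure came, and the 12-month cut discards that. If instead few continue-arm patients flare, arm explains most of the variation, and a model without arm leaves it as noise around every biomarker effect. The two situations call for different halves of the same remedy.

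Predictors of recurrence are a stated secondary objective (Protocol 1.1) and the subject of directional hypotheses (Protocol 4.1, hypothesis 2). SAP 3.1.2 itself regards P-values after model selection as doubtful, so the single-predictor step is where effect estimates are most readable. If that step is weak, real predictors are more likely to be reported as showing no association.

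**Working it through.** **Inputs from the SAP.** Section 3.3.1: "A sample size of 118 subjects (59 in each group) provides 88% power to detect a hazard ratio of 2.0", "assuming a median time until treatment failure of 10 weeks in the group that discontinues adalimumab (Arm 1) and of 20 weeks" in the continue group, "an equal allocation between groups, and a 10% total loss to follow-up", and "We assume an alpha of 0.05 (two sided"). Follow-up is 48 weeks and the dropout rate 0.0022 per week (SAP 13.1). Visits are at weeks 4, 8, 12, 16, 24, 32, 40 and 48 (Protocol 1.3).

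**The plan's own figure.** The formula is N = (Zα+Zβ)²(φ(λC)+φ(λI))/(λI−λC)², with λ = ln2/10 and ln2/20, and T = 48. It gives 52.9 per group for 88% power. Allowing for loss, 2 × 52.9/0.9 = 117.6, so 118. The 88% reproduces.

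**Failure by 12 months at the design medians.** 1−2^(−48/10) = 96.4% in the stop arm and 1−2^(−48/20) = 81.1% in the continue arm. These are treatment failures, which include arthritis failures.

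**What a hazard ratio of 2.0 becomes on the yes/no scale.** Give half the patients hazard × √2 and half hazard ÷ √2 within each arm:
- lower-risk half: (90.5% + 69.2%)/2 = 79.8%
- higher-risk half: (99.1% + 90.5%)/2 = 94.8%
- relative risk: 94.8/79.8 = 1.19

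With 53 per half, the two-proportion power is Φ[(0.150×√53 − 1.96×√(2×0.873×0.127)) / √(0.798×0.202+0.948×0.052)] = Φ(0.37) = 64%. With 59 per half it is 69%.

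**The same effect on the time scale.** Schoenfeld's formula is power = Φ(√d/2 × ln2 − 1.96). About 100 events give Φ(1.51) = 93%, and 50 events give Φ(0.49) = 69%.

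**Simulation.** 118 patients, 50:50 predictor, hazard ratio 2.0, exponential failure times recorded at scheduled visits, 10% exponential loss, Efron ties. Patients lost before an event are left out of the yes/no model. Poisson regression with robust variance stands in for the log binomial model (it is the SAP 3.2.2 fallback). Ranges cover repeat runs, some with continuous failure times.

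| 12-month failure, stop / continue | Yes/no, no arm | Yes/no + arm | Cox, no arm | Cox + arm |
|---|---|---|---|---|
| 96% / 81% (design medians) | 66–67% | 68–69% | 88–89% | 92–93% |
| 80% / 52% (SAP 3.3.2.1: 80%, less the 28-point detectable difference) | 70–71% | 73% | 80% | 82–85% |
| 80% / 10% (about 50 flares, SAP 3.3.2.2; the 10% is assumed) | 29–30% | 54% | 35–38% | 67–68% |

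In the last row, 59×0.80 + 59×0.10 = 53 flares before loss and about 50 after. In the middle row, front-loading failures (70% and 42% by 6 months) gives 71% against 80%.

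**Where the gain comes from.** At the design medians, moving to time without arm adds about 22 points, and arm then adds about 4. At about 50 flares, adding arm to the yes/no model adds about 24 points, and time then adds about 13. Time without arm adds only 5 to 8 there. Ties matter because failures fall on visit dates: with Breslow handling, the 93% in the first row drops to about 87%.

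**The case against.** The strongest case against is that little is missing. Time to failure is a listed Aim 2 objective, and a Cox LASSO with arm among the candidates is planned. Aim 2 is called exploratory, so power at 0.05 is a loose yardstick. Occurrence by 6 and 12 months is the named outcome, so fixed-horizon risk answers the stated question. Version 5 of the SAP postdates unmasking, so changing the lead analysis now is post hoc. All of this stands. It reduces the point to which analysis leads and whether arm is always in the model. It does not remove the gain, which appears under every event assumption tried.

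A reader might infer more than the documents support:
- **That the SAP credits the opening model with 88% power.** It does not. SAP 3.3.2.2 ties the 88% to the time-to-failure outcome, so that figure needs no relabelling.
- **That 80% flaring caps any relative risk at 1.25.** This holds only if 80% is the reference group's risk. An average of 80% in a 50:50 split can be 60% against 100%, a relative risk of 1.67.
- **That omitting arm confounds the predictors.** Baseline predictors are balanced across arms in expectation by randomization. The loss is of power.
- **That timing always carries most of the information.** At about 50 flares most of the gain comes from arm.

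**Conclusion.** The point holds as one of precision in an exploratory aim. For a 50:50 predictor with hazard ratio 2.0, the opening Aim 2 model gives up about 26 points of power at the design medians (67% against 93%). The loss is about 12 points at 80%/52% failing (70% against 82%), and about 37 points at about 50 flares (30% against 67%).

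The size rests on proportional hazards, a predictor independent of arm, and N = 118. The third figure also rests on my assumed 10% continue-arm rate. The SAP's own event assumptions differ from section to section, so none of the three can be called its single expectation. Enrollment stopped at the interim, so realised power will differ. SAP section 12 records a treatment effect much larger than anticipated, which makes the arm-adjustment half the more relevant one.

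Separately, SAP 2.3.2 (treatment failure) and SAP 3.1.2 (uveitis flare) name different lead outcomes for Aim 2.

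**What to change.** In SAP 3.1.2:
- Add randomized arm to every single-predictor model.
- Run a Cox model for each predictor, with arm as covariate or stratum and Efron ties, censored at 12 months and again at 6 months. Lead with these.
- Force arm, unpenalised, into the LASSO and Cox LASSO.
- Keep the log binomial models, with arm, as supportive, so that 6- and 12-month risks are still reported.
- Name one Aim 2 outcome and use it in both 2.3.2 and 3.1.2.
- Record the change in the revision history as made after the interim, as was done for the Cox analyses added to Aim 3 in SAP 3.1.3.

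The cost is SAP wording and some code, with no new data or patients. There are two downsides: the lead measure becomes a hazard ratio, which is less direct for counselling than a risk, and the change is post-interim and must be reported as such. The supportive models largely offset the first.
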